The flowchart of the study is presented in Figure 1. Randomization was carried out among the 23 priority districts in this study with a ratio of 2:1 (that is, 2 intervention districts per 1 control district). The details of randomization are explained in section B.4 of this document. **The assigned 15 intervention districts and 8 comparison districts** are described in Table 6. Potential participants in the intervention area will be screened through the inclusion and exclusion criteria established for

this study. The criteria for participants who are eligible for this study are explained in section B.3 of this document and Annex2.

According to the Indonesian Ministry of Health's current recommendation, HIV blood test at an authorized health facility is still the current practice for HIV diagnosis. Both participants in the intervention and comparison area will be offered for HIV blood test at a health facility. Participants in comparison areas and participants in intervention areas who agree to take HIV test at a health facility will then be managed further according to the existing guideline or "standard of care." For participants in intervention areas who refuses to have her blood drawn for HIV test at a health facility will then be offered self-testing using OraQuick®. Participants will then fill and sign the informed consent to participate in CBS study.

Next, participants will be offered to do the test assisted or unassisted. If the participant chooses to perform the test assisted, the PL/PE will help her from filling in a baseline survey, performing the test, and filling in a post-test survey. If the participant chooses to perform the test unassisted, there will be two options for the participant to get the test kit. First, PL/PE will deliver the test kit for the participant, help with filling in the baseline survey on the spot and give information about uploading test results and the post-test survey, along with a hotline number to call for any questions and concerns, including follow-up steps after participants have received the results. The second method, participants will be given a link online which will entitle information of this study, eligibility criteria, informed consent, baseline survey, link to order a test kit, link to upload result and link to fill in the post-test survey. Participant who chooses this second method will also be given hotline number should there be any further inquiries.

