
3. Implementation Guidelines: Unassisted Community Screening

Because of differences in the structure of sex work and in the enabling environment in different districts, it will be necessary to develop the details of unassisted community screening on a district-by-district basis. Ideally, the same unassisted community screening intervention would be implemented in the same way in all intervention districts, but if this is not possible due to the factors outlined above, allowing some details to vary across districts is preferable to trying to implement a standard protocol that is expected a priori to fail in some locations.

For unassisted community screening, in which OW don't have face-to-face contact with FSWs, possible mechanisms for distributing Ora-Quick test kits entail:

- a. Trained PE/PL identifying various online networks in which FSWs use to solicit their service.
- b. Trained PE/PL building trust from FSWs to participate in the study.
- c. Trained PE/PL send broadcast message containing brief information of the study, eligibility criteria for participation, step-by-step method to order the kit and have it delivered to their address, short link for description of how to use the kit (flier or short video), and mandatory baseline and post-test survey. Test kit delivery will be done by same-day delivery system (Go-Send/Grab Send) from selected places where the test kit will be stored (Implementing Unit Office or selected health care facilities) to client's address. Trained peer leader/peer educator could also distribute the test kit but not participating in the testing by assisting FSW during the test.

- d. Trained PE/PL carrying out follow-up for FSWs being previously approached for the test. The same trained PE/PL is assigned to be the contact person/hotline for each FSW they approached and agreed to take the test.
- e. FSW send/upload results of the test along with a completed post-test survey. Cash (mobile top-up) incentive will be transferred to FSW who send the test results and post-test survey. Every kit distributed will have unique code and FSW will be asked to fill it in both baseline and post-test survey to ensure one FSW is entitled to only one test kit.

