Except for outreach, all above mentioned activities are incentivized. Below are details of incentives given to PL/PE based on current standard program:

1. Cash incentive of 70,000 IDR for every client who referred for HIV testing to health facilities.
2. Cash incentive of 25,000 IDR for every client taking the test after being reached through mobile outreach.
3. Cash incentive of 50,000 IDR for every client with positive confirmatory test starting on ART.

5. Incentives for Participation

Incentives will be given for different participation role in this study:

1. For all eligible FSWs participating in baseline survey will be given 50,000 IDR
2. For FSWs taking VCT and reporting the results will be given 100,000 IDR
3. For FSWs doing CBS AND uploading/sending test result will be given 100,000 IDR
4. For FSWs participating in post-test survey (both assisted and unassisted) will be given 50,000 IDR
5. Cash incentive 100,000 IDR for transportation and registration and/or fee for confirmatory test for CBS **reactive result** for FSWs who go to health care facility for confirmatory test (assisted and unassisted)
6. Cash incentive 100,000 IDR for transportation and registration and/or fee for confirmatory test for CBS **non-reactive result** for FSWs who go to health care facility for confirmatory test (assisted and unassisted)

Incentives will be given for different role of PL/PE in this study:

1. For PL/PE who assists FSWs for taking self-screening (including filling in baseline and post-test) will be given 150,000 IDR
2. For PL/PE who delivers test kit to FSWs who opt for unassisted screening AND obtain baseline survey on the spot will be given 100,000 IDR

Incentives will be given for health facility:

For collecting data on FSWs who do confirmatory test (assisted and unassisted). Funds to cover additional operational cost will be given to each implementing unit (IU) for delivering test kit via Go-Pay/Grab Pay Top-Up to client's address.

D. LINKAGE TO HEALTH SERVICES FOR ARV INITIATION

Outreach workers will navigate clients to health care facilities for confirmatory test and ARV initiation if the result is confirmed as positive. Health care facilities in each district will be selected by their readiness to offer Test & Treat (T&T). Clients who come for confirmatory test are expected to be started for ARV initiation on the same day of confirmatory test.

E. DATA COLLECTION PROTOCOLS

1. Baseline survey

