4. Numbering System for Test Kit and Other Instruments

a) Recording Test Kit ID

Every test kit will have a unique ID number, which will later be referred to as the Kit ID number. The Kit ID Number is to be filled in on all instruments and forms that are to be linked to the test results (e.g., baseline survey, test results form, post-test survey, routine data record in each IU, etc.). This number needs to be identified at all times to make sure that each participant is only assigned to one test kit, matching the kit with the results, and to track the stock of the test kit remained. The format of this ID kit will be “01-001”, where the first 2 digits are to identify the number of the district in which participants take the test, and the last 3 digits are to identify which test kit the participant is using. This test kit ID will also be later used for each IU to track the distribution of the test kit. Every test kit being distributed, either in a fixed place or delivered through same-day delivery services, will be recorded and tracked by each IU. An MS Excel or MS Access form will be developed to record and track the Kit ID Number.

b) Recording temporary FSW ID

On the ground of confidentiality, participants' full name will not be revealed and used within this study. A new system to ensure the reliable yet confidential identification of study participants needs to be established. Every participant in the study will be assigned to a temporary FSW ID. The format will be **the first 4 letters of participants' names added by the date of birth (yy/mm/dd)**. For example, a participant named “INDRIYANTI” who was born on March 5th 1976, her temporary FSW ID will be “INDR760305”. For FSW whose name contains only 3 letters, the number zero will be added after the last letter. For example, an FSW whose name is “AYU” and was born on March 5th 1976, her temporary will be “AYU0760305”. This temporary FSW ID will be used to ensure that each participant is only assigned to one test kit, to track test results, and to be filled in the baseline and post-test survey.

c) Matching Test Kit ID and temporary FSW ID

To match the test kit ID and temporary FSW ID, an automatic system needs to be developed to detect it precisely. This way, we can be sure that each participant only gets to participate in this study once (from receiving the kit, performing the test, and reporting the result).

d) Paper Based Data Collection

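### Online kit orders pay 200,000 IDR remotely, and the only person-level duplicate check is a self-declared name fragment and birth date, so altered or invented entries could be counted as separate women

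*Combined protocol and SAP*

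**What the plan says.** **Route.** B.1 (Design Summary) gives the second unassisted option as a "link online which will entitle information of this study, eligibility criteria, informed consent, baseline survey, link to order a test kit", followed by links to upload the result and complete the post-test survey. C.1 confirms that this needs no contact with an outreach worker. Under section H, consent for unassisted screening is a tick box. Under C.3, the kit travels by same-day courier.

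**Payment.** C.3(e): "Cash (mobile top-up) incentive will be transferred to FSW who send the test results and post-test survey". C.5 lists the amounts:
- "For all eligible FSWs participating in baseline survey will be given 50,000 IDR"
- "For FSWs doing CBS AND uploading/sending test result will be given 100,000 IDR"
- "For FSWs participating in post-test survey (both assisted and unassisted) will be given 50,000 IDR"
- "Cash incentive 100,000 IDR for transportation and registration and/or fee for confirmatory test for CBS", for reactive and non-reactive results alike.

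**Identity control.** E.4(b) builds the temporary FSW ID from "the first 4 letters of participants' names added by the date of birth (yy/mm/dd". The survey forms in Annexes 6 and 8 accept either a full name or initials. C.3(e) and E.4(a) give each kit a unique code, which the implementing unit (IU) tracks. E.4(c) calls for an automatic match of kit ID to FSW ID, still to be built, and concludes that "we can be sure that each participant only gets to participate in this study once".

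**Analyses.** F.3 divides confirmatory tests by women who received the self-test, assisted versus unassisted. F.4 divides women tested, self-tests included, by women offered a test, intervention versus control. Section F has no rule for duplicates and no sensitivity analysis for them.

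**The concern.** The kit code identifies the kit, not the woman. Online, the baseline survey is also listed ahead of the kit order. What identifies the woman is therefore only what she types. Someone who re-enters the same details should be caught by the planned match. Someone who changes a letter or a day, or invents both, becomes a new participant with a new kit and a new set of payments. No check on phone number, payment account, delivery address or identity is described for this route.

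The errors would not cancel. A false record counts as tested, and self-testing exists only in intervention districts, so F.4 would tend to rise in that arm alone. A false record that never attends a facility enlarges the F.3 denominator in the unassisted group, so unassisted screening would tend to look worse at getting women to a facility. F.3 answers the assisted-versus-unassisted question, which is one of the five primary objectives.

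**Working it through.** **Payment per online kit** (C.5). Remote steps: 50,000 + 100,000 + 50,000 = 200,000 IDR. With a confirmatory visit: 200,000 + 100,000 = 300,000 IDR.

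**The plan's sample size** (B.5), used below only as the group size. With proportions 0.5 and 0.6, average 0.55 and 90% power, a one-sided 5% test needs 423 per group. Then 423 x 1.5 = 634.5, or 635, and 634.5 x 1.2 = 761.4, or 761. The plan's figures are thus reproduced. The printed Z of 1.96 with the full multiplier of 1.5 gives 777 before the allowance. That is a separate matter, and nothing here depends on it.

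**F.3.** Let a be true facility attendance, the same for both methods, and f the share of all unassisted records that are false and never attend. Observed unassisted attendance is a(1 - f). The documents give no value for f, so 5%, 10% and 20% are assumed. Two values of a are shown: 60%, which is B.5's planning value for facility testing in intervention districts, and 20%, an assumption. The lower value is shown because women offered the self-test have just declined a facility test.

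Effective size per group: 761 / 1.5 = 507.3. For a two-sided 5% test, with p1 = a, p2 = a(1 - f), d = p1 - p2 and p the average of p1 and p2:
- se0 = sqrt(2p(1 - p) / 507.3)
- se1 = sqrt((p1(1 - p1) + p2(1 - p2)) / 507.3)
- chance of a spurious difference = Phi((d - 1.96 se0) / se1), plus the opposite tail, which is small

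Example, a = 60% and f = 10%: p2 = 0.54, p = 0.57, se0 = 0.03108, se1 = 0.03103. Then (0.06 - 1.96 x 0.03108) / 0.03103 = -0.03, and the chance is 0.49.

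| f | Observed, a = 60% | Spurious difference | Observed, a = 20% | Spurious difference |
|---|---|---|---|---|
| 5% | 57.0% | 16% | 19.0% | 7% |
| 10% | 54.0% | 49% | 18.0% | 13% |
| 20% | 48.0% | 97% | 16.0% | 38% |

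A fall of 10 points, the difference the trial is sized for, needs f = 0.10 / 0.60 = 17% at a true 60%.

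Because f covers all unassisted records, including kits handed over by peer workers, the rate among online orders must be higher. If half of unassisted kits were ordered online (assumption), f = 10% means 20% of online orders are false.

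**F.4.** Table 5 sums to 36,979 outreach contacts a year over the 15 intervention districts. Over the 7 intervention months: 36,979 x 7/12 = 21,571. Take 20% of 761 = 152 false records, all counted as tested, and an assumed true uptake of 50%.
- All contacts offered a test: (10,785.5 + 152) / (21,571 + 152) = 50.3%, a rise of about 0.3 points.
- A quarter offered (5,393): (2,696.4 + 152) / (5,393 + 152) = 51.4%, a rise of about 1.4 points.

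**The case against.** The strongest reply is that duplicate control is planned and unfinished. There are unique kit codes on both surveys, IU tracking of every kit including courier deliveries, an automatic match yet to be developed, and a follow-up peer worker for each woman approached. The system could still use phone number and address. This stands in part: identical re-entries should be caught, and C.3's follow-up contact is a partial human check. But the matching rule as written rests on the temporary ID, and the follow-up contact is tied to women whom a peer worker approached.

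The payment structure also cuts both ways. A confirmatory visit pays a further 100,000 IDR after either result, so some repeat entrants may attend. Lower attendance is therefore likely, not certain.

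Three stronger readings are tempting, and the documents do not support them:
- **That false entries are in fact distorting the results.** No false-entry rate is given. The percentages above are a range, not a forecast.
- **That assisted screening will look better than it is.** Assisted participants earn the same 200,000 IDR under the same kind of ID, and the peer worker earns 150,000 IDR per assisted screen. An incentive to over-count exists there too. Only the absence of contact is peculiar to the online route.
- **That positivity (F.6) is diluted.** A repeat entry by one woman may simply repeat her screening result. The direction depends on whether positivity means self-test reactive or facility-confirmed.

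**Conclusion.** The point holds as a gap in the identification rule. For no-contact online orders, a self-declared name fragment and birth date cannot support E.4(c)'s assurance of single participation, because the other controls follow kits rather than women. Entrants who alter or invent their details could be counted as separate women.

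The comparison at risk is F.3. Its exposure depends strongly on two unknowns, the share of false records and true attendance: at f = 10%, the chance of a spurious difference is 49% at 60% attendance and 13% at 20%. These figures assume that false records never attend, that true attendance is equal in the two groups, and that the plan's design effect of 1.5 applies to this comparison. F.4 is likely to be affected little at the trial's outreach scale. It would be wrong to read this point as showing that the intervention-versus-control uptake result is an artefact of duplicates.

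**What to change.** In E.4(b)-(c) and C.3, add the mobile top-up number, stored hashed, to the matching rule. Each online or courier order then releases one kit and one set of payments per number. Flag repeat delivery addresses for a check. In section F, state that F.3 to F.7 count de-duplicated women, not kits or temporary IDs. Report F.3 and F.4 again without online orders. That analysis is supportive only, because it drops the harder-to-reach women whom this route is meant to serve.

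The cost is a rule in a system still to be built and a few lines of analysis text, using data already needed for payment and delivery. Women who share a phone will need manual clearance, and one more linked identifier must be protected. The control is partial, since a second SIM would evade it. The rule should be in place before kits are sent, because duplicates may be hard to separate afterwards.

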1.1 Recruitment of study personnel										
1.2 Ethics and permit										
1.3 Stakeholders mapping and engagement strategy										
1.4 Procurement of test kit										

Activities	Month									
	Feb	March	April	May	June	July	Aug	Sept	Oct	Nov
1.5 Development of manual of operating procedure (SOP, questionnaire, study media, website, WhatsApp center, CRF forms)										
2.Implementation training										
3.Intervention										
3.1 Study kick-off										
3.2 Data collection										
4. Data analysis and report writing										
5. Workshop for study finding dissemination										

3. Eligibility Criteria

The target audience for the intervention to be evaluated are FSW in Intervention districts that meet the criteria outlined below.

Inclusion criteria

- Women, 18 years or older at enrolment
- Reports transactional sex (vaginal, oral and/or anal) at least once in the past month
- No HIV test in last 6 months
- Self-reported HIV negative OR HIV status unknown

Exclusion criteria

- Unwilling to participate for any reason
- Concurrently participating in another HIV prevention study

4. Randomization

Stratified randomization was carried out for the 23 priority districts involved in this study. First, sampling strata were created by sorting the mean average value of achieved HIV testing target per semester from 2018-2019 in each district from the largest to the smallest. The second step was to sort the districts into eight groups of three districts, except for the last group which will only consist of two districts. Randomization for intervention and comparison group were then carried out within these groups of eight with 2:1 ratio (2 intervention: 1 comparison).² The results of stratified randomization are presented in Table 6. In separate table, Table 7 contains 15 intervention districts and Table 8 contains 8 comparison districts.

² A 2-to-1 intervention to comparison district ratio was chosen in order to increase the likelihood of recruiting a sufficient number of FSW for community screening to reach the sample size target considering the relatively short time frame available for for study implementation.

Table 6. Allocated intervention group and comparison group

No	Kab/Kota	Region	Achieved target of HIV testing per semester (2018-2019)	Group
1	Kota Denpasar	3	982	Intervention
2	Kota Makassar	3	866	Comparison
3	Kota Palembang	1	694	Intervention
4	Kota Jakarta Utara	1	612	Comparison
5	Kota Medan	1	575	Intervention
6	Kota Surabaya	3	568	Intervention
7	Kota Jakarta Barat	1	544	Intervention
8	Kota Bandung	2	487	Comparison
9	Kota Jakarta Timur	1	479	Intervention
10	Kota Jakarta Pusat	1	473	Intervention
11	Kota Jakarta Selatan	1	448	Comparison
12	Kota Sorong	4	415	Intervention
13	Kab. Tangerang	1	391	Intervention
14	Kota Bogor	2	374	Intervention
15	Kota Jayapura	4	323	Comparison
16	Kota Bandar Lampung	1	319	Comparison
17	Kota Depok	2	287	Intervention
18	Kota Malang	3	243	Intervention
19	Kota Tangerang Selatan	1	184	Intervention
20	Kota Bekasi	2	158	Comparison
21	Kota Surakarta	2	144	Intervention
22	Kota Semarang	2	129	Comparison
23	Kab. Deli Serdang	1	80	Intervention

Table 7. Allocated intervention districts

No	Kab/Kota	Region	Achieved target of HIV testing per semester (2018-2019)	Group
1	Kab. Deli Serdang	1	80	Intervention
2	Kota Medan	1	575	Intervention
3	Kota Palembang	1	694	Intervention
4	Kab. Tangerang	1	391	Intervention
5	Kota Tangerang Selatan	1	184	Intervention
6	Kota Jakarta Barat	1	544	Intervention
7	Kota Jakarta Pusat	1	473	Intervention
8	Kota Jakarta Timur	1	479	Intervention
9	Kota Bogor	2	374	Intervention
10	Kota Depok	2	287	Intervention
11	Kota Surakarta	2	144	Intervention
12	Kota Surabaya	3	568	Intervention
13	Kota Malang	3	243	Intervention
14	Kota Denpasar	3	982	Intervention
15	Kota Sorong	4	415	Intervention

Table 8. Allocated comparison districts

No	Kab/Kota	Region	Achieved target of HIV testing per semester (2018-2019)	Group
1	Kota Bandar Lampung	1	319	Comparison
2	Kota Jakarta Utara	1	612	Comparison
3	Kota Jakarta Selatan	1	448	Comparison
4	Kota Bekasi	2	158	Comparison
5	Kota Semarang	2	129	Comparison
6	Kota Bandung	2	487	Comparison
7	Kota Makassar	3	866	Comparison
8	Kota Jayapura	4	323	Comparison

5. Recruitment and Sample Size

All FSW in intervention districts who meet study eligibility criteria will be offered community screening (see Section C below for intervention implementation guidelines). FSW in comparison districts will continue to receive the current standard package of interventions.

In to be able to detect a 10 percentage point difference in the rate of HIV testing at health facilities between FSW in intervention vs. comparison districts and have 95% certainty that a difference of that magnitude would not have occurred by chance and 90% certainty of detecting a difference of this magnitude if the difference was real/”the truth,” the following sample of FSW will be needed in intervention and in comparison districts:³

$$n \geq [Z_{1-\alpha} (2P(1-P))^{1/2} + Z_{1-\beta} (P_1(1-P_1) + P_2(1-P_2)^2 / (P_1-P_2)^2)] * deft$$

Where:

$Z_{1-\alpha}$ = the Z score for the level of statistical confidence, or statistical precision, desired (for 95%, $Z = 1.96$)

$Z_{1-\beta}$ = the Z score for the desired statistical power (for 90% one-sided test, $Z = 1.282$)

P_1 = the expected population proportion in the comparison group of districts (set = 0.5 – this is the worst-case scenario and will produced a sample size that is adequate irrespective of the actual proportion)

P_2 = the expected population proportion in the intervention group of districts (set = 0.6 – assume minimum effect size to be realized of 10 percentages points)

$$P = (P_1 - P_2) / 2$$

$(P_1 - P_2)$ = the magnitude of comparison-group differences (or change over time) to be detected with the specified level of precision and power (assumed to be +/- 10 percentage points)

deft = design effect to compensate for clustering at the district level (1.5 assumed).

The required sample size is thus $n \geq 635$ per experimental group; ≥ 761 after 20% allowance for lost-to-follow up

³ Source: Lwanga SK and Lemeshow S. Sample Size Determination in Health Studies: A Practical Manual. Geneva: World Health Organization.

Interpretation: we would need to recruit 761 FSW who self-test for HIV testing in the intervention districts and 761 FSW for HIV testing at health facilities in comparison districts to be able to detect a 10 percentage point difference in the rate of HIV testing at health facilities (intervention vs. comparison districts) to have 95% certainty that a difference of that magnitude would not have occurred by chance and 90% certainty of detecting a difference of this magnitude if such a difference existed.

In order to assess whether “assisted” or “unassisted” community HIV screening among FSW results in a larger increase in the rate of HIV testing at health facilities, we would need samples of size $n \geq 761$ each of FSW who received assisted and unassisted screening in intervention districts, a total of $n \geq 1,522$ FSW in intervention districts, plus $n \geq 761$ in comparison districts.

Sample size requirements for the third question measurement pertains to the number of FSW who test positive for HIV at a health facility and are thus eligible to initiate treatment. This will depend upon (1) the number of FSW presenting at health facilities for testing and (2) the positivity rate among those tested. Sample sizes should thus be calculated accordingly. If we assume a testing positivity rate of 3%, it is apparent that the expected number of FSWs who would be eligible for treatment will be small and we will lack sufficient statistical power to make meaningful comparisons with comparison districts. For this reason, it is recommended that the impact of community screening among FSW be measured using SIHA data for FSW in both intervention and comparison districts. This estimate of impact derived in this way will be confounded if it were to be the case that interventions other than HIV self-testing were to be better implemented in intervention vs. comparison districts. It might be possible to minimize this potential bias by including measures of intervention implementation performance in the intervention and comparison districts in multivariable analyses. Thus, a large enough sample size is required to ensure sufficient power to determine the difference in the intervention and control districts.

C. THE INTERVENTION

1. General Description of The Intervention

FSW who meet the eligibility criteria will be offered for HIV blood test first. Participants who wish to take the test will then managed according to the current guideline for standard of care. Participants who disagree to take HIV blood test will then be offered screening test with Ora-Quick®. There will be with two options for community HIV screening by Peer Leaders: (1) in a convenient community setting assisted by PL/PE (assisted screening) or (2) in a setting of their own choosing without assistance from PL/PE (unassisted screening). FSW will also be able to access a community-based screening test by following online link from messages spread through WhatsApp number without having to come into contact with outreach workers. The saliva-based Ora-Quick® test kit will be used for community screening.

The community screening intervention will be implemented as an additional component to be added in intervention districts to the intervention package currently being implemented by UNFPA's Implementation Units (IUs). In “control districts” implementation of the UNFPA-supported GFATM will proceed without modification as concerns community screening.

2. Implementation Guidelines: Assisted Community Screening

For assisted community screening, which can only be undertaken with FSW with whom outreach worker (OW) have established face-to-face contact, the standard outreach process will entail:

- a. For FSW that have not been tested for HIV for at least six (6) months at the time of outreach contact, (i) recommend HIV testing at a health facility, (ii) offer to facilitate making an appointment for testing to accompany them to a health facility for testing, and (iii) provide FSW

with a referral card to be submitted to the health facility in order to help track numbers of FSW that were tested for HIV.

- b. For those that refuse or decline to go to a health facility for testing, offer community HIV screening and explain the process and benefits.
- c. For those who decline community screening, remind them of the need for periodic testing to protect their health and offer to assist them with health facility testing and/or community screening at a later date.
- d. For those who accept community screening, explain the test procedure and assist the client to perform the test providing as much assistance as is needed and/or requested, especially regarding interpreting the result.
- e. For clients with reactive community screening results, (i) advise them to get a confirmatory test at a health (ii) offer to facilitate making an appointment for testing to accompany them to a health facility for testing, and (iii) provide FSW with a referral card to be submitted to the health facility.
- f. For clients with non-reactive community screening results, (i) remind them of the need for protective behaviors (i.e., condom and lubricant use, periodic STI screening), (ii) remind them of the need for periodic HIV testing and reinforce prevention measures and (iii) offer a referral card in case FSW want a confirmatory test at a health facility (if there is concern about the accuracy of the community screening test).
- g. The current procedures for tracking whether FSW were tested, and if positive for HIV had initiated treatment, will be unaffected by the community screening study.

3. Implementation Guidelines: Unassisted Community Screening

Because of differences in the structure of sex work and in the enabling environment in different districts, it will be necessary to develop the details of unassisted community screening on a district-by-district basis. Ideally, the same unassisted community screening intervention would be implemented in the same way in all intervention districts, but if this is not possible due to the factors outlined above, allowing some details to vary across districts is preferable to trying to implement a standard protocol that is expected a priori to fail in some locations.

For unassisted community screening, in which OW don't have face-to-face contact with FSWs, possible mechanisms for distributing Ora-Quick test kits entail:

- a. Trained PE/PL identifying various online networks in which FSWs use to solicit their service.
- b. Trained PE/PL building trust from FSWs to participate in the study.
- c. Trained PE/PL send broadcast message containing brief information of the study, eligibility criteria for participation, step-by-step method to order the kit and have it delivered to their address, short link for description of how to use the kit (flier or short video), and mandatory baseline and post-test survey. Test kit delivery will be done by same-day delivery system (Go-Send/Grab Send) from selected places where the test kit will be stored (Implementing Unit Office or selected health care facilities) to client's address. Trained peer leader/peer educator could also distribute the test kit but not participating in the testing by assisting FSW during the test.

- d. Trained PE/PL carrying out follow-up for FSWs being previously approached for the test. The same trained PE/PL is assigned to be the contact person/hotline for each FSW they approached and agreed to take the test.
- e. FSW send/upload results of the test along with a completed post-test survey. Cash (mobile top-up) incentive will be transferred to FSW who send the test results and post-test survey. Every kit distributed will have unique code and FSW will be asked to fill it in both baseline and post-test survey to ensure one FSW is entitled to only one test kit.
- f. For clients with reactive community screening results, (i) advise them (online) to get a confirmatory test at selected health facility (ii) offer to facilitate making an appointment for testing to accompany them to a health facility for testing, and (iii) provide FSW with a referral card to be submitted to the health facility. Another possible option is to have the referral cards within the test kit, therefore when FSW with reactive results do not wish for their result to be revealed other than towards the post-test survey platform and health officers, they can access health facility for confirmatory test. Information on what's needed to be done when one finds reactive test result has to be mentioned in detail within the instructional fliers or video.
- g. For clients with non-reactive community screening results, (i) again online reinforce prevention measures, (ii) remind them of the need for periodic testing and (iii) offer a referral card in case FSW want a confirmatory test at a health facility (if there is concern about the accuracy of the community screening test). In the case where referral card is included within every box containing test kit, FSW with non-reactive result might still be able to bring the card to selected health facility to get a confirmatory test.

4. Implementation Guidelines for Control Group (Standard Program)

For the control group, there will be no new interventions implemented (that is, they will continue with “business as usual”). In each control site, there is an implementing unit (IU) responsible for conducting outreach for FSWs. The outreach target is set up for one year, meaning that a sex worker will only be outreached once in a year. The outreach packet should include condoms and lubricant distribution as well as HIV-AIDS education media distribution. Furthermore, each IU also has a certain number of HIV tests to fulfill every six months. To achieve the target, the IU should reassure sex workers to do HIV test at least once every six months. While it is possible for a sex worker to have HIV test in three months interval, only one test is count for a sex worker every six months. The test could be conducted at health facilities or mobile clinics. A mobile clinic could be conducted at any place where convenient to the participants, such as workplace or living space. For FSWs with reactive test results, they will then be referred to health facility to start on ART.

Except for outreach, all above mentioned activities are incentivized. Below are details of incentives given to PL/PE based on current standard program:

1. Cash incentive of 70,000 IDR for every client who referred for HIV testing to health facilities.
2. Cash incentive of 25,000 IDR for every client taking the test after being reached through mobile outreach.
3. Cash incentive of 50,000 IDR for every client with positive confirmatory test starting on ART.

5. Incentives for Participation

Incentives will be given for different participation role in this study:

1. For all eligible FSWs participating in baseline survey will be given 50,000 IDR
2. For FSWs taking VCT and reporting the results will be given 100,000 IDR
3. For FSWs doing CBS AND uploading/sending test result will be given 100,000 IDR
4. For FSWs participating in post-test survey (both assisted and unassisted) will be given 50,000 IDR
5. Cash incentive 100,000 IDR for transportation and registration and/or fee for confirmatory test for CBS **reactive result** for FSWs who go to health care facility for confirmatory test (assisted and unassisted)
6. Cash incentive 100,000 IDR for transportation and registration and/or fee for confirmatory test for CBS **non-reactive result** for FSWs who go to health care facility for confirmatory test (assisted and unassisted)

Incentives will be given for different role of PL/PE in this study:

1. For PL/PE who assists FSWs for taking self-screening (including filling in baseline and post-test) will be given 150,000 IDR
2. For PL/PE who delivers test kit to FSWs who opt for unassisted screening AND obtain baseline survey on the spot will be given 100,000 IDR

Incentives will be given for health facility:

For collecting data on FSWs who do confirmatory test (assisted and unassisted). Funds to cover additional operational cost will be given to each implementing unit (IU) for delivering test kit via Go-Pay/Grab Pay Top-Up to client's address.

D. LINKAGE TO HEALTH SERVICES FOR ARV INITIATION

Outreach workers will navigate clients to health care facilities for confirmatory test and ARV initiation if the result is confirmed as positive. Health care facilities in each district will be selected by their readiness to offer Test & Treat (T&T). Clients who come for confirmatory test are expected to be started for ARV initiation on the same day of confirmatory test.

E. DATA COLLECTION PROTOCOLS

1. Baseline survey

